8.5 Stopping Rules.....	36
8.6 Medical Monitoring	36
9.0 Data Handling and Record Keeping	36
9.1 Confidentiality	36
9.2 Source Documents	37
9.3 Case Report Forms.....	37
9.4 Records Retention.....	37
10.0 Study Monitoring, Auditing, and Inspecting	37
10.1 Study Monitoring Plan.....	37
10.2 Auditing and Inspecting.....	38
11.0 Ethical Considerations	38
12 Study Finances	39
12.1 Funding Source	39
12.2 Conflict of Interest	39
12.3 Subject Stipends or Payments	39
13 Publication Plan	39
14 References.....	39
15 Attachments	40

List of Abbreviations

AE	Adverse Event
CFR	Code of Federal Regulations
CRF	Case Report Form
FDA	Food and Drug Administration
GCP	Good Clinical Practice
HIPAA	Health Insurance Portability and Accountability Act of 1996
ICH	International Conference on Harmonization
IDS	Investigational Drug Service
IRB	Institutional Review Board
ITT	Intent to Treat
NCCPC-R	Non-Communicating Children's Pain Checklist-Revised
PHI	Protected Health Information
REPA	Report of External Professional Activities
SAE	Serious Adverse Event
UPIRTSO	Unanticipated Problems Involving Risk to Subjects or Others

Study Summary

Title	A phase II, randomized, placebo-controlled, double blind, cross-over, study of the effects of Gabapentin on chronic irritability in neurologically impaired children
Short Title	Effects of Gabapentin on chronic irritability in neurologically impaired children.
Phase	Phase II
Methodology	The study is a randomized, placebo-controlled cross-over.
Study Duration	The estimated duration of the study is 12 months
Study Center(s)	This is a single center study to be conducted at Gillette Children's Specialty Hospital, [name].
Objectives	To determine if gabapentin provides symptom relief for chronic irritability in neurologically impaired children despite medical management for identified sources of symptoms or if no etiology is identified.
Number of Subjects	40 evaluable subjects
Diagnosis and Main Inclusion Criteria	Neurological impairment and chronic irritability suggesting pain.
Study Product, Dose, Route, Regimen	Gabapentin (Neurontin®), to be administered as an oral solution titrated over a 22 day period, followed by a 7 day stable dose period (40 mg/kg/day over 3 dosages), followed by a 9 day taper and washout period
Duration of administration	Subjects will receive drug for 34 days, and placebo for 34 days, with a 3 day washout period in between.
Reference therapy	Reference therapy for this study is the placebo as there is no standard of care.
Statistical Methodology	The study will utilize non-parametric descriptive statistics to compare subject questionnaire responses after drug and placebo exposures.

Formatted: Highlight

Formatted: Highlight

Formatted: Highlight

Formatted: Highlight

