Gabapentin did not demonstrate mutagenic or genotoxic potential in three *in vitro* and four *in vivo* assays. It was negative in the Ames test and the *in vitro* HGPRT forward mutation assay in Chinese hamster lung cells; it did not produce significant increases in chromosomal aberrations in the *in vitro* Chinese hamster lung cell assay; it was negative in the *in vivo* chromosomal aberration assay and in the *in vivo* micronucleus test in Chinese hamster bone marrow; it was negative in the *in vivo* mouse micronucleus assay; and it did not induce unscheduled DNA synthesis in hepatocytes from rats given gabapentin.

Gabapentin has been shown to be fetotoxic in rodents, causing delayed ossification of several bones in the skull, vertebrae, forelimbs, and hindlimbs. These effects occurred when pregnant mice received oral doses of 1000 or 3000 mg/kg/day during the period of organogenesis, or approximately 1 to 4 times the maximum dose of 3600 mg/day given to epileptic patients on a mg/m² basis. The no-effect level was 500 mg/kg/day or approximately 1/2 of the human dose on a mg/m² basis.

When rats were dosed prior to and during mating, and throughout gestation, pups from all dose groups (500, 1000 and 2000 mg/kg/day) were affected. These doses are equivalent to less than approximately 1 to 5 times the maximum human dose on a mg/m² basis. There was an increased incidence of hydroureter and/or hydronephrosis in rats in a study of fertility and general reproductive performance at 2000 mg/kg/day with no effect at 1000 mg/kg/day, in a teratology study at 1500 mg/kg/day with no effect at 300 mg/kg/day, and in a perinatal and postnatal study at all doses studied (500, 1000 and 2000 mg/kg/day). The doses at which the effects occurred are approximately 1 to 5 times the maximum human dose of 3600 mg/day on a mg/m² basis; the no-effect doses were approximately 3 times and approximately equal to the maximum human dose on a mg/m² basis. Other than hydroureter and hydronephrosis, the etiologies of which are unclear, the incidence of malformations was not increased compared to controls in offspring of mice, rats, or rabbits given doses up to 50 times (mice), 30 times (rats), and 25 times (rabbits) the human daily dose on a mg/kg basis, or 4

times (mice), 5 times (rats), or 8 times (rabbits) the human daily dose on a mg/m² basis.

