1.5 Dose Rationale and Risk/Benefits

The dose protocol (see Section 5.2.) is based upon ideal dosing ranges, with sensitivity paid to titrating up and down slowly to minimize potential side effects and withdrawal symptoms. Additionally, the rationale of the increased dose in the evening is related to the known effect of inducing tiredness in some individuals. The decision to use the liquid form is to allow for tight titration of medications, and to prevent the need for "pill-splitting" to achieve precise dosing. Additionally, the liquid form may be easy to administer to patients with gastrostomy tubes. Finally, the liquid form will also be better tolerated by those patients without gastrostomy tubes but have difficulty manipulating pills.

Potential risks of Gabapentin include (from most common to least common): somnolence, dizziness, increase in hostility, nausea/vomiting, increased chance for viral infections and fevers, ataxia, fatigue, emotional lability, increased weight, and hyperkinesia.

Risks to unborn children are unknown. Therefore, parents of females who have reached puberty will be asked to allow a pregnancy test to be done. If applicable, a urine pregnancy test will be done on Day 0.

There is a risk for loss of privacy; however, study personnel will take precautions to prevent loss of privacy.

The risks of the medication are expected to be minimal compared to the benefit of relief from distressing symptoms (neuroirritability). Establishment of Gabapentin as an effective therapy for neuroirritability will help many children in the future be appropriately treated for the underlying condition without the need for other more dangerous medications (benzodiazepenes).

The patient population for this study is comprised of severely cognitively and often developmentally impaired children. Therefore, it is not applicable to screen for suicidality in this population.

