4.0 Subject Selection and Withdrawal

4.1 Inclusion Criteria

Subjects are eligible to participate in the study if all of the following conditions exist:

1. Male or female, age 1 month to 16 years at enrollment
2. Neurological impairment defined as subnormal (-2 S.D.) motor and/or cognitive ability from a variety of etiologies
3. Chronic irritability defined as symptoms suggesting pain to the child's caregiver occurring recurrently over a 4-week or greater time period
4. Subject must have an acceptable surrogate capable of giving consent on the subject's behalf

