4.2 Exclusion Criteria

Subjects will be excluded from participation in the study if any of the following conditions exist:

1. Children with resolved symptoms after treatment of identified sources
2. Identified potential source of irritability without adequate trial of appropriate management
3. Ketogenic diet
4. Renal insufficiency or failure
5. Current treatment with gabapentin or pregabalin for another existing condition

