5.2 Treatment Regimen

Doses will be given in liquid form through gastrointestinal tubes (if the child already has one) or orally. Children will be put on the following dosage regimen:

Day	Morning	Afternoon	Evening
1 - 3			5 mg/kg
4 - 6	2.5 mg/kg	2.5 mg/kg	5 mg/kg
7 - 9	2.5 mg/kg	2.5 mg/kg	10 mg/kg
10 - 12	5 mg/kg	5 mg/kg	10 mg/kg

13 - 15	5 mg/kg	5 mg/kg	15 mg/kg
16 - 18	7.5 mg/kg	7.5 mg/kg	15 mg/kg
19 - 21	7.5 mg/kg	7.5 mg/kg	20 mg/kg
22 - 28	10 mg/kg	10 mg/kg	20 mg/kg
29	7.5 mg/kg	7.5 mg/kg	20 mg/kg
30	7.5 mg/kg	7.5 mg/kg	15 mg/kg
31	5 mg/kg	5 mg/kg	15 mg/kg
32	5 mg/kg	5 mg/kg	10 mg/kg
33	2.5 mg/kg	2.5 mg/kg	10 ing/kg
34			5 ing/kg

35 - 37 off for 3 days then crossover

Weight			
Day	Morning	Afternoon	Evening
1 - 3			5 mg/kg
4 - 6	2.5 mg/kg	2.5 mg/kg	5 ing/kg
7 - 9	2.5 mg/kg	2.5 mg/kg	10
10 - 12	5 mg/kg	5 mg/kg	10 mg/kg
13 - 15	5 mg/kg	5 mg/kg	15 ing/kg
16 - 18	7.5 mg/kg	7.5 mg/kg	15 mg/kg
19 - 21	7.5 mg/kg	7.5 mg/kg	20 mg/kg
22 - 28	10 mg/kg	10 mg/kg	20 mg/kg
29	7.5 mg/kg	7.5 mg/kg	20 mg/lcg
30	7.5 mg/kg	7.5 mg/kg	15 mg/kg
31	5 mg/kg	5 mg/kg	15 mg/kg
32	5 mg/kg	5 mg/kg	10 mg/kg

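### The weight-based schedule has no stated daily maximum, so an eligible child over 90 kg would be scheduled above the 3600 mg/day that section 1.3 cites as the human maximum

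*SAP*

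**What the plan says.** The Study Summary describes titration "followed by a 7 day stable dose period (40 mg/kg/day over 3 dosages"). Section 5.2 introduces its table with "Children will be put on the following dosage regimen" and gives every row in mg/kg, peaking at 10, 10 and 20 mg/kg on days 22-28. Section 5.9.3 also prescribes by weight and turns the result into volumes at 50 mg/ml on a chart made for each child.

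Section 4.1 admits "Male or female, age 1 month to 16 years at enrollment". Section 4.2 opens "Subjects will be excluded from participation in the study if any of the following conditions exist" and lists five conditions. Neither section limits weight.

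Section 1.3 names 3600 mg/day twice when it scales animal exposures: as "the maximum dose of 3600 mg/day given to epileptic patients", and again in "approximately 1 to 5 times the maximum human dose of 3600 mg/day". Section 1.4 lists 3600 mg/day as the highest target dose in the postherpetic neuralgia studies. Section 1.5 gives this justification for the regimen: "The dose protocol (see Section 5.2.) is based upon ideal dosing ranges". On the pace of dose changes, the same section adds "with sensitivity paid to titrating up and down slowly to minimize potential side effects and withdrawal symptoms". It does not mention a daily maximum.

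**The concern.** A mg/kg rule with no upper bound gives a daily dose that rises with weight without limit. For most children this has no consequence. For a heavy adolescent, a pharmacy that follows section 5.2 exactly would prepare a dose above the highest human dose the document cites, and the document gives no reason for going beyond it. What is at stake is the exposure of an individual child for several days in the active period. The treatment comparison is not at stake.

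**Working it through.** **Inputs**
- Peak row, section 5.2, days 22-28: 10 + 10 + 20 = 40 mg/kg/day. This reproduces the Study Summary figure.
- Next-highest rows, days 19-21 and 29: 7.5 + 7.5 + 20 = 35 mg/kg/day.
- Reference figure, section 1.3: 3600 mg/day.
- Solution strength, section 5.9.3: 50 mg/ml.
- Number of subjects, Study Summary: 40.
- Weights: none are given, so those below are illustrations.

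**Weight at which a row passes 3600 mg/day** (3600 divided by mg/kg/day)
- 40 mg/kg rows: 3600/40 = 90 kg.
- 35 mg/kg rows: 3600/35 = 102.9 kg.
- 30 mg/kg rows (days 16-18 and 30): 3600/30 = 120 kg.

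**Scheduled dose** (mg/kg × weight)

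| Weight | Days 22-28 | Days 19-21 and 29 | Days above 3600 mg/day |
|---|---|---|---|
| 90 kg | 3600 mg | 3150 mg | 0 |
| 100 kg | 4000 mg (+11%) | 3500 mg | 7 |
| 110 kg | 4400 mg (+22%) | 3850 mg (+7%) | 3 + 7 + 1 = 11 |

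**With the early taper.** Section 6.0 starts the taper early if there is no improvement at Day 24. Assuming it starts on Day 25, a 100 kg child has 3 days above 3600 mg/day (days 22-24). A 110 kg child has 3 (days 19-21) + 3 (days 22-24) + 1 (first taper day) = 7. A child who is improving completes the whole peak week.

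**Reach.** For assumed shares over 90 kg of 0%, 1% and 2.5%, the expected number is 40 × 0 = 0, 40 × 0.01 = 0.4 and 40 × 0.025 = 1.

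**Effect of calculating on at most 90 kg**
- Peak: 900 + 900 + 1800 = 3600 mg/day, or 18 + 18 + 36 = 72 ml/day.
- Days 19-21 and 29: 675 + 675 + 1800 = 3150 mg/day, so Day 29 is still a step down of 3600 - 3150 = 450 mg/day.
- Effective peak: 3600/100 = 36 mg/kg/day at 100 kg; 3600/110 = 32.7 at 110 kg.
- Earlier steps also fall. At 100 kg, days 16-18 go from 3000 to 30 × 90 = 2700 mg/day, and days 1-3 from 500 to 5 × 90 = 450 mg/day.

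**The case against.** The strongest reply is that the document contains no error here. The Study Summary and section 5.2 agree on 40 mg/kg/day. Section 1.3 uses 3600 mg/day only to scale animal doses, and section 1.4 lists it as a target dose in another condition. A reader might infer that the plan breaks its own dose limit, or that a dose above 3600 mg/day is shown to be unsafe. The text supports neither reading: the figure is never adopted as a ceiling for this trial, and nothing in the document bears on harm above it. That part of the reply stands.

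It also stands that the dosing chart, listed as an attachment, is not shown and may already hold a maximum; that no weight data show any child to be affected; and that protections exist. Titration moves in 3-day steps, renal insufficiency is excluded, phone checks fall on Days 6, 13, 24 and 28 of the first period with similar contacts in the second, and side effects lead to an unscheduled examination. These limit the consequence but do not bound the dose.

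A further objection is that capping the dosing weight reduces doses on all 34 days, including days that never approach 3600 mg/day. That is true. A flat ceiling of 3600 mg/day would touch fewer days but would flatten the steps: at 110 kg, days 19-21, 22-28 and 29 would all become 3600 mg/day, with no increase on Day 22 and no reduction on Day 29. Given the emphasis in section 1.5 on slow changes, the weight cap is the better trade.

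**Conclusion.** The point holds as an inexpensive improvement of low priority. As written, the visible text would schedule an eligible child over 90 kg above 3600 mg/day on days 22-28 and, above 102.9 kg, also on days 19-21 and 29. The excess is 11% at 100 kg and 22% at 110 kg.

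The thresholds and day counts are exact. The reach rests on assumed weight shares, and 0 to 1 of 40 subjects is an illustration whose range includes none. The conclusion also assumes that the chart carries no ceiling. A reader might infer that the efficacy comparison or the sample size is compromised; it is not, because section 7.1 does not depend on the absolute dose and so few children could be involved.

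**What to change.** - **Section 5.2 and the dosing-chart template:** add *Doses are calculated on actual weight or 90 kg, whichever is lower.* Apply it in both periods, using the weight taken for that period, and identically to placebo volumes so that the blind is kept.
- **Section 6.0, Day 24 early-taper rule:** change the dose condition to *40 mg/kg/day or the capped dose*. A capped child never reaches 40 mg/kg/day, so the present condition would be ambiguous for that child.
- **Study Summary regimen:** add *maximum 3600 mg/day*.
- **If the chart already has a ceiling:** state that ceiling in section 5.2 instead. The sponsor's clinicians may choose a lower one.

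The cost is three short text edits and one limit in the chart template. Doses at or below 90 kg, the timing of titration and taper, the sample size and the analysis do not change. The downside is that children over 90 kg receive less than 40 mg/kg/day and proportionally less at every step, so any benefit that depends on the full mg/kg dose could be smaller in them.

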1.0 Introduction

This document is a protocol for a human research study. This study is to be conducted according to US and international standards of Good Clinical Practice (21 CFR 312 and International Conference on Harmonization guidelines), applicable government regulations and Institutional research policies and procedures.

1.1 Background

Irritability in nonverbal neurologically impaired children (neuro-irritability) is often considered to indicate pain in such children. Children with neurological impairment experience pain more frequently than the general pediatric population¹. In one study, 44% of children with severe cognitive impairment were reported by caregivers to experience pain each week during a four-week interval. Pain frequency was highest in the most impaired group of children.² Caregivers of children with moderate to severe cerebral palsy reported over a 4-week interval that 26% experienced pain or discomfort "once or twice", 19% "a few times", 10% "fairly often", 2.5% "very often", and 8% "every/almost every day".³ In a study of nonverbal cognitively impaired children, caregivers reported that 62% experienced five or more separate days of pain, and 23.5% experienced pain almost daily.⁴

Identifying a source of pain in a nonverbal child with neurological impairment poses a unique and significant challenge. Common recognized pain sources in these individuals include acute sources such as fracture, urinary tract infection, or pancreatitis and chronic sources such as gastroesophageal reflex (GER), constipation, feeding difficulties from delayed gut motility, positioning, spasticity, hip pain, or dental pain. Table 1 outlines etiologies of acute and chronic pain to consider.

Pain in neurologically impaired children is typically thought to be nociceptive in origin. Experience shows that a pain source may not be identified or pain may continue despite treatment of an identified source. Greco et al⁵ identified the category "Screaming of unknown origin" to indicate children with neurologic disorders, severe developmental delay, neurodegeneration, or severe motor impairments with persistent agitation, distress, or screaming. Evaluation may identify a specific nociceptive cause but in many other cases, these evaluations can be frustrating for patients, families, and clinicians. In the chapter "Pain and Children with Developmental Disabilities", Oberlander and Craig review that pain in neurologically impaired children is typically thought to be nociceptive in origin; however, after repeated injury or surgery, neuropathic pain may also occur.⁶ Because of the confusing neurologic and clinical picture, identification of neuropathic pain is challenging. Neuropathy may be another source of ongoing and poorly treated pain in such children.

Parents commonly identify the gastrointestinal tract as a source of pain in neurologically impaired children. Breau et al⁷ identified gastrointestinal as the second most common pain source category, after accidental causes, yet the most frequent source of all episodes of pain in children with severe cognitive impairment. Roughly half with gastrointestinal pain experienced pain classified as 'bowels' but not due to constipation and a similar number experienced episodes classified as 'digestive' due to 'gas' or 'gastrointestinal' problems without identification of cause or 'location. Pain of unknown cause was the most intense, followed by pain attributed to the bowels, gastrointestinal tract and digestive pain. Houlahan et al³ reported significantly higher rates of pain in children with a gastrostomy tube and those taking medications for feeding, gastroesophageal reflux or gastrointestinal motility.

Table 1. Etiology of pain/irritability in nonverbal neurologically impaired children

Head, Eyes, Ears, Nose, Throat (HEENT)
Acute otitis media, pharyngitis, sinusitis, dental abscess/gingival inflammation, corneal abrasion, glaucoma, ventriculoperitoneal shunt malfunction
Chest
Pulmonary aspiration/pneumonia, esophagitis, pericardial effusion, supraventricular tachycardia, cardiac ischemia
Abdomen
Gastrointestinal: gastroesophageal reflux disease, gastritis/gastric ulcer, peptic ulcer disease, food allergy, appendicitis, intussusception, constipation, delayed/impaired motility, rectal fissure, visceral hyperalgesia
Liver/gallbladder: hepatitis, cholecystitis
Pancreas: pancreatitis
Renal: urinary tract infection, nephrolithiasis, neuropathic bladder, obstructive uropathy
Genitourinary: inguinal hernia, testicular torsion, ovarian torsion/cyst, menstrual cramps
Skin
Pressure sore/decubitus ulcer
Extremities
Fracture, hip subluxation, osteomyelitis, hair tourniquet
Psychosocial
Loss of caregiver, change in home environment, non-accidental trauma
General
Medication toxicity, sleep disturbance

[figure not shown]
The association between pain and the gastrointestinal tract led to speculation that visceral hyperalgesia is a source of chronic irritability and agitation in neurologically impaired children. Zangen et al⁸ identified visceral

hyperalgesia as a source of feeding difficulty in 12 of 14 neurologically impaired children with refractory, persistent food refusal, retching and vomiting despite maximal medical therapy and Nissen fundoplication. All patients had gastrointestinal motility and/or sensory abnormalities. Twelve of the 14 patients showed a low threshold for gastrointestinal sensory symptoms. Seven patients demonstrated both motility and sensory impairment. Only two patients had abnormal motility without sensory involvement. Tricyclic antidepressants and gabapentin successfully managed the symptoms identified in these patients. In a retrospective series of nine neurologically impaired children who experienced significant unexplained pain and irritability, marked symptom improvement was identified when the children received gabapentin therapy titrated to standard doses.⁹ For such children with persistent irritability, we suggest use of medications, such as gabapentin, that have demonstrated benefit for neuropathic pain syndromes.

Gabapentin is a medication utilized for treating neuropathic pain and has the safest side effect profile of medications used for neuropathic pain. These investigators have observed benefit without harm in use of gabapentin for neurologically impaired children with chronic irritability. There is no standard of care for this problem.

1.2 Investigational Agent

Gabapentin (Neurontin®) is described as 1-(aminomethyl)cyclohexaneacetic acid with a molecular formula of C₉H₁₁NO₂ and a molecular weight of 171.24. The structural formula of gabapentin is:

Gabapentin is a white to off-white crystalline solid with a pK_{a1} of 3.7 and a pK_{a2} of 10.7. It is freely soluble in water and both basic and acidic aqueous solutions. The log of the partition coefficient (n-octanol/0.05M phosphate buffer) at pH 7.4 is —1.25. The oral solution contains 250 mg/5 mL of gabapentin. The inactive ingredients for the oral solution are glycerin, xylitol, purified water and artificial cool strawberry anise flavor.

The mechanism by which gabapentin exerts its analgesic action is unknown, but in animal models of analgesia, gabapentin prevents allodynia (pain-related behavior in response to a normally innocuous stimulus) and hyperalgesia (exaggerated response to painful stimuli). In particular, gabapentin prevents pain-related responses in several models of neuropathic pain in rats or mice (e.g. spinal nerve ligation models, streptozocin-induced diabetes model, spinal cord injury model, acute herpes zoster infection model). Gabapentin also decreases pain-related responses after peripheral inflammation (carrageenan footpad test, late phase of formalin test).

Gabapentin did not alter immediate pain-related behaviors (rat tail flick test, formalin footpad acute phase, acetic acid abdominal constriction test, footpad heat irradiation test). The relevance of these models to human pain is not known.

The mechanism by which gabapentin exerts its anticonvulsant action is unknown, but in animal test systems designed to detect anticonvulsant activity, gabapentin prevents seizures as do other marketed anticonvulsants. Gabapentin exhibits antiseizure activity in mice and rats in both the maximal electroshock and pentylenetetrazole seizure models and other preclinical models (e.g., strains with genetic epilepsy, etc.). The relevance of these models to human epilepsy is not known.

All pharmacological actions following gabapentin administration are due to the activity of the parent compound as gabapentin is not appreciably metabolized in humans. Adult subjects with compromised renal function require dosage adjustment. Pediatric subjects with renal insufficiency have not been studied. Dosage adjustment is also required for subjects undergoing hemodialysis. The apparent oral clearance of gabapentin decreased with increasing age, largely due to age related decline in renal function. Although formal studies comparing gender and race have not been studied, no significant gender or race differences are expected.

